# **STUDY PROTOCOL**

## 1. Research Design

**Overall study aim:** This will be a pragmatic, patient-randomized controlled effectiveness trial. We will randomize up to 455 overweight and obese adult participants to a 12-month weight gain prevention intervention (Balance, or *Equilibrio* in Spanish) or to usual care. Our primary outcome will be weight gain prevention over 24 months, defined as  $\leq 3\%$  change in initial body weight over 24 months. We will gather all follow-up patient data to assess outcomes from their Piedmont electronic health record. We will not have any intervention contact with participants during the final 12 months, with the exception of a Balance intervention satisfaction survey. Funding for this trial was provided by the National Institutes of Health, National Institute of Diabetes and Digestive and Kidney Diseases on May 13, 2016. Funding continued through April 30, 2023.

**Background:** Up to 50% of obese patients are not interested in, or ready for, weight loss. Clinical practice guidelines clearly recommend that these patients avoid gaining weight. Doing so might contain, or even attenuate, the adverse cardiometabolic risks that accrue with additional weight gain. However, despite this clinical guideline, weight gain prevention interventions are not available in primary care practice. This evidence gap disproportionately affects medically vulnerable patients -- those who are low-income, often racial/ethnic minority, and may reside in rural settings. These patients have the highest rates of obesity and weight gain, but the least interest in, readiness for, and success with weight loss. The implications for these patients are clear: without intervention, most will continue to gain weight and incur cardiometabolic risks. For obese medically vulnerable patients, weight gain prevention is a priority but treatment options do not exist.

**Pragmatic Effectiveness Trial:** This will be a pragmatic effectiveness trial to test the Balance intervention in rural community health centers. We will randomize up to 455 overweight and obese adults to either: 1) usual care, or 2) a 12-month weight gain prevention intervention, including mHealth self-monitoring and feedback, skills training videos, and responsive coaching from a clinic dietitian. Our primary outcome is weight gain prevention at 24 months.

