Per the request of Piedmont Health, to collect our evaluation data from the EHR, we will provide Piedmont Health with lists of enrolled participants in a spreadsheet format for whom we need pre-baseline and follow-up data for Balance evaluation purposes. The participants will be identified in spreadsheets with their names, dates of birth, and Piedmont Health patient ID numbers (which will be extracted from our Balance Duke REDCap project for enrolled participants) to ensure we are receiving the correct participant data from the record. These spreadsheets will only be stored and accessed within a restricted Duke-provisioned Box folder and within a protected subfolder with restricted access granted to the necessary personnel at Piedmont Health and the Duke research team. Piedmont Health will directly upload the evaluation reports into this designated Duke Box folder, or will send the reports via their encrypted email system to the Balance study coordinator. If securely emailed, the Balance study coordinator will access the encrypted files, promptly save the reports in the designated Duke Box folder and delete the emails. When subsequent analyses are conducted by the Balance biostatisticians utilizing these datasets, the names, dates of birth and Piedmont Health patient ID numbers will be redacted, and only study IDs will be used to identify participants.

The processes for data collection and data elements that will be collected from the participant's medical record will be explained to the participant as part of the consent process (See Appendix A) and in the written HIPAA Authorization Form (See Appendix D). At the 12-month timepoint, we will mail a completion letter in English or Spanish to active study participants and provide a certificate of completion

or a revised letter thanking them for their participation (if they were in the program for at least 6 months but may not have completed the full 12 months of Balance). (See Appendix O). We will not have any intervention contact with participants during the final 12 months.

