## **STATISTICAL ANALYSIS PLAN**

## Statistical Analysis Plan

Baseline variables were summarized by the intervention arm as means and SDs for continuous variables and as counts and percentages for categorical variables. We used a 2-stage modeling strategy to answer our primary hypothesis. All analyses were intent-to-treat. For the first stage, we estimated the intervention effect on weight using a constrained longitudinal linear mixed effects model, using all available data from between 18 months pre-enrollment through 30.5 months postenrollment. We explored nonlinearities for the fixed effects of time and random effects of time in the models, guided by the Bayesian Information Criterion and likelihood ratio tests. The model included fixed effects for time and interactions between time segments and intervention, with a random intercept and random slopes for time. The covariance between random effects was modeled using an unstructured covariance matrix. Randomization was stratified by CHC; thus, we adjusted for CHC in the analyses but did not adjust for other variables. Using this linear mixed effects model, we estimated mean weight change by intervention arm, and the difference between intervention arms in mean weight change, at 6, 12, 18, and 24 months.

Second, we compared the percentage of  $\leq 3\%$  weight gain, our primary outcome, in each arm at 24- months postrandomization using individual empirical best linear unbiased predictors (EBLUPs) from the mixed model. To ensure good predictions, we only used individual EBLUPs from participants with at least 1 EHR weight documented within a 6-month window centered on the 24-month time point (ie, between 21 and 27 months postenrollment). We compared the percentage of  $\leq 3\%$  weight gain in intervention and usual care arms using both a log-binomial model and linear risk model on the EBLUP output, in order to obtain both risk ratios and risk differences, which provide estimates of relative and absolute efficacy, respectively. The extra variability induced by the EBLUPs being predicted from the model was taken into account using a resampling procedure, explained further in the Multimedia Appendices 1 and 2. Sensitivity to the 21- to 27-month window was assessed by obtaining predictions after expanding the window. We additionally used EBLUPs to compare the percentage of  $\leq 3\%$  weight gain in each arm at 6-, 12-, and 18-months postrandomization.

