Additional sensitivity analyses included adjusting the model for baseline variables imbalanced across arms, by weight measured in the primary time window ( $P < .10$ ) and removing telehealth visits from the analysis. We also explored effect modification by adding interactions to the primary model with age tertiles; gender; BMI class; race and ethnicity; and preferred language (English or Spanish), each in a separate model. Additionally, in post hoc analyses we added the completion date of the study (pre- or post-COVID) as an effect modifier to examine the potential impact of COVID-19 on the intervention effect.

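### The SAP labels every analysis intent-to-treat, but the primary ≤3% risk ratio and risk difference cover only participants with a chart weight at 21 to 27 months, and no all-randomised version is described

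*Combined protocol and SAP*

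**What the plan says.** The Statistical Analysis Plan opens with a general claim: "All analyses were intent-to-treat". It then describes two stages.

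- **Stage 1** is a constrained longitudinal mixed model for weight, "using all available data from between 18 months pre-enrollment through 30.5 months postenrollment". It yields mean weight change by arm at 6, 12, 18 and 24 months.
- **Stage 2** is the primary outcome. Each person is classified as having gained ≤3% or not from the individual prediction (EBLUP) of the stage 1 model. The reason given for the restriction is prediction quality: "we only used individual EBLUPs from participants with at least 1 EHR weight documented within a 6-month window centered on the 24-month time point". The log-binomial model (RR) and the linear risk model (RD) are fitted to that output. Prediction uncertainty is carried forward: "The extra variability induced by the EBLUPs being predicted from the model was taken into account using a resampling procedure".

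Two sensitivity analyses bear on the restriction. One varies the window: "Sensitivity to the 21- to 27-month window was assessed by obtaining predictions after expanding the window". The other is "adjusting the model for baseline variables imbalanced across arms, by weight measured in the primary time window". A third removes telehealth visits.

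On where the weights come from, section 1 of the protocol says "We will gather all follow-up patient data to assess outcomes from their Piedmont electronic health record". On contact after the 12-month intervention it says "We will not have any intervention contact with participants during the final 12 months", a satisfaction survey aside.

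**The concern.** Whether someone has a chart weight near month 24 is settled after randomisation. Conditioning on it means that the two groups compared in stage 2 are no longer the two randomised groups, even though each person stays in the assigned arm. Nothing suggests exclusion for poor adherence or crossover. The fault is narrower: an unqualified label, and no check that covers everyone randomised.

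Stage 1 is not affected, but it estimates mean weight change, not the primary RR and RD. A reader who takes the label at face value will apply the RR and RD to all randomised patients. The SAP text neither commits to reporting window counts by arm nor gives an all-randomised estimate of the ≤3% outcome against which to judge the restriction.

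**Working it through.** **1. The passages side by side.** The label covers all analyses. The stage 2 restriction covers the primary RR and RD. The expanded window has no stated width and still requires a recorded weight. The baseline adjustment changes covariates and returns nobody to the comparison. Removing telehealth visits can only take weights away. None of the three is described as covering everyone randomised.

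**2. Size of a possible bias.** In one arm let p be success among all randomised, f the share without a window weight, and g success with a window weight minus success without one. Then p = (success with) − f·g, so success in the subset is p + f·g. Hence

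RD in subset − RD in all randomised = f1·g1 − f0·g0.

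This is zero when f and g are equal across arms.

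**3. Inputs.** The documents give no window coverage, so every f and g below is an assumption. Section 1 cites retention in the 90% range in earlier work, and section 2 plans for 15% with no data past baseline. Neither is window coverage; they only suggest trying f = 10% and 15%.

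| Assumed case | Bias in RD (points) |
|---|---|
| g = 10 in one arm, 0 in the other, f = 10% | 0.10 × 10 = 1.0 |
| same, f = 15% | 0.15 × 10 = 1.5 |
| g = +10 and −10, f = 10% | 0.10 × 20 = 2.0 |
| same, f = 15% | 0.15 × 20 = 3.0 |
| g = 10 in both arms, f = 15% v 10% | 1.5 − 1.0 = 0.5 |

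**4. Scale.** The planned 221 per group reproduces as 192 × 1.15 = 220.8. Classified per arm: 221 × 0.90 = 199 or 221 × 0.85 = 188. The standard error of the RD is √(2p(1−p)/n), before the added prediction variance:

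- p = 0.8, n = 199: 4.01 points
- p = 0.5, n = 188: 5.16 points

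The smallest ratio among the one-arm and opposite-sign cases is 1.0/5.01 = 0.2 (p = 0.5, n = 199). The largest is 3.0/4.13 = 0.7 (p = 0.8, n = 188).

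Section 2 also assumes 5% loss per month. If that loss were permanent and compounded to month 21 on top of the 15%, then f = 1 − 0.85 × 0.95^21 = 71%, and g = 10 in one arm would give 7.1 points. That is an extreme reading: the figure was set for a time-to-event calculation, and gaps in clinic weights may be intermittent.

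**5. What an all-randomised analysis would do.** This is a simulation in which all inputs are assumed: 400,000 per arm; baseline 90 kg (SD 15); slope 0.5 kg/year (SD 2); residual SD 2 kg; weights at months −12, −6, 0, 6, 12 and 18, plus month 24 for those with a window weight; model parameters known. Latent draws means sampling each person's error-free baseline and 24-month weights from the model's conditional distribution.

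- *No selection, 2 kg effect (success about 82% v 66%).* Windowed EBLUPs give RD 16.3 to 16.4. Latent draws give 15.8 in the windowed subset and 15.8 in all randomised. Draws that include residual error give 13.9 to 14.0. Comparing EBLUPs with draws therefore shows a gap of 0.5, or 2.3 to 2.4 with residual error, when there is no selection at all.
- *Identical arms, the same selection in both* (log-odds of no window weight 0.4 per SD of observed 0 to 18 month gain). The gap between windowed and all-randomised draws is 0.0.
- *Identical arms, that selection in one arm only* (g about 11). The gap is 1.1 points at f = 10% and 1.7 at f = 15%, against 1.1 and 1.6 from the formula. All-randomised draws give 0.1 and 0.2 against a true RD of 0.1 and 0.1.
- *Delta shift of 1, 2 and 3 kg in that arm.* The all-randomised RD moves by 1.0, 2.0 and 2.9 points at f = 10%, and by 1.5, 3.0 and 4.3 at f = 15%.

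**The case against.** The strongest reply has four parts.

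**The label is only loose, and nothing is hidden.** The window and its reason appear in the same section as the label, and people are analysed as assigned. This is fair. It supports keeping the windowed analysis as primary, but not the unqualified label.

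**Checks already exist.** The expanded window may recover many people, since stage 1 data run to 30.5 months, and the baseline adjustment is aimed at selection into the window. Both count as partial checks. Neither is described as reaching everyone randomised, and a wider window cannot reach anyone with no later weight. Multimedia Appendices 1 and 2, which the SAP cites for the resampling, were not available, so the absence of an all-randomised version is established only for the text at hand.

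**There is little reason to expect different selection by arm.** Both arms use the same health record, weight is measured at every visit, and the window opens 9 months after the intervention ends. The documents describe no arm-specific reason for having a window weight. This stands and is why bias is called possible only. The 2.0 and 3.0 point cases need selection in opposite directions.

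**The remedy is imperfect, and a simpler one might do.** If excluded people have no weight after baseline, all-randomised draws keep most of the bias: about 0.8 points at f = 10% and 1.1 or slightly more at f = 15%, under the one-arm selection above. This is correct, and it is why a delta shift is needed. Dropping the window and reusing EBLUPs works about as well when people have weights to month 18. For people with no post-baseline weight, however, EBLUPs shrink toward the mean and class 76% as successes when the true figure is 66%, so draws are preferable.

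**Conclusion.** The concern holds. As written, the intent-to-treat statement is wrong for the primary RR and RD, which rest on a subset formed after randomisation. The text available describes no all-randomised analysis of the ≤3% outcome.

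The consequence is uncertain and probably modest. Under the main assumed cases the RD could be off by 1.0 to 3.0 points (0.2 to 0.7 of a standard error), and by nothing if coverage and selection are alike in the two arms. These sizes rest on assumed f, g and success rates and would grow if window coverage were much lower than 85%. The stage 1 mean-weight results are not in question. The point should be fixed because a stated property of the primary analysis is inaccurate and a borderline result could be sensitive to it.

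**What to change.** 1. Describe stage 2 as an as-randomised, available-data analysis.
2. Report by arm the number randomised and the number with a 21 to 27 month weight.
3. Keep the windowed analysis as primary and report beside it one all-randomised sensitivity analysis of the ≤3% outcome. For each person, draw latent baseline and 24-month weights, without residual error, from the stage 1 model's conditional distribution, allowing for parameter uncertainty. Classify each draw, fit the RR and RD models, and combine across draws.
4. Apply the same draw-based classification in the windowed subset, so that a difference from step 3 reflects the population and not the classifier.
5. Add a delta shift, for example 0, 1, 2 and 3 kg, to the drawn 24-month weights of those without a window weight, in one arm and then in both. Report where the conclusion changes. The kg values are illustrative, as the documents give no basis for a range.
6. Label the additions post hoc if the analysis has been run. The SAP is in the past tense, so this is likely.

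The cost is modest programming on data already held, since the stage 1 model and a resampling procedure exist. The relabelling and the counts cost almost nothing. The all-randomised interval will be somewhat wider. For people without late weights the draws rely on missing at random and on the form of the model, which step 5 is there to probe.

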**Usual Primary Care Condition:** Usual Primary Care participants will receive the standard primary care offered by their providers; mailed study materials (pedometer, self-help materials such as NHLBI's "Aim for a Healthy Weight"); as well as automated (non-tailored) text messages with health information/skills training for six months. At least annually, our team presents an update on obesity treatment at a medical staff meeting attended by all providers. We will conduct these trainings at study kickoff, and will continue them throughout the trial. We will not influence usual primary care in any other way.

**Weight Gain Prevention Intervention Condition:** Intervention participants will receive: 1) tailored behavior change goals, 2) self-monitoring using connected scales and mobile technologies, 3) responsive coaching, and 4) tailored feedback and skills training. We describe each below:

**iOTA — the interactive obesity treatment approach (iOTA):** We developed iOTA and have used it in several recent primary care-based obesity treatment trials. iOTA creates an energy deficit by having participants achieve simple, straightforward, and concrete behavior change goals (e.g., no fast food, no sugary drinks, walk 10k steps per day). We designed iOTA in response to the frequent finding of poorer trial outcomes and less intervention engagement among medically vulnerable populations when traditional weight loss intervention approaches are used. We think that traditional treatments are less successful in the medically vulnerable because of their literacy/numeracy requirements, cognitive complexity, and resource assumptions. In contrast, iOTA is straightforward and does not require expert knowledge or expensive resources. Participants simply take a short survey, are assigned tailored behavior change goals, self-monitor their adherence to those goals using their phones,

and receive immediate tailored feedback, regular skills training, and dietitian counseling that is informed by their tracking data.

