At Piedmont, weight and blood pressure are measured at all visits, including for acute care. Our proposed lab tests are also commonly administered. We will closely monitor patients' medical visits during the 24 to 30-month follow-up period. We have extensive experience retaining medically vulnerable patients, consistently reporting retention rates in the 90% range. We are thus confident that we will have adequate follow-up data to conduct our outcome analyses.

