## **2. Subject Selection**

**Inclusion Criteria:** The study involves males and females aged  $\geq 21$  years who are English and Spanish-speaking patients at a Piedmont Health Services primary care health center; and with a BMI between 25-40 kg/m^2 and weight less than 380 pounds. Eligible participants will have had a non-urgent visit to a Piedmont Health clinic within the last 2 weeks. Eligible participants will also have a cell phone and be willing to receive study-related text messages (3-12 messages per week).

**Exclusion Criteria:** Potential participants cannot: be a current Piedmont Health employee; currently or recently (within the past six months) pregnant or planning on becoming pregnant in the next 12 months; be currently or recently (past 2 months) lactating; have prior or planned bariatric surgery; have a diagnosis contraindicating weight loss (e.g., active malignancy); have a history of a cardiovascular event (stroke, MI); or have been hospitalized for a mental health issue in the last 12 months; have a diagnosis of end-stage kidney disease (ESRD) in the medical record; or due to investigator discretion for a potential health or safety issue. Potential participants who have a history of a coronary artery revascularization (in last 12 months) will be allowed to participate in the study with provider approval (See Appendix C).

**Sample size:** We will recruit up to 455 adult men and women, who speak either English or Spanish. At least 30% of the sample will be male (we recently recruited a 31% male sample in Track). The sample size calculation is based on the primary aim examining differences in the time to gain  $\geq 3\%$  of baseline weight between intervention and control groups. Based on Shape's clinical data, we assume a 5% sample loss for each group per month of the study. A sample of N=192 per group (Total N=384) allows us to test the difference between the two distributions with greater than 80% power. Factoring in an additional expected sample loss of 15% (those with no clinical data past baseline) gives a final sample size of N=221 per group (Total N=442, with the possibility of enrolling up to 455).

For the qualitative Balance implementation sub-study, we will recruit up to 25 Piedmont Health employees in varying roles and across the participating sites and leadership team.

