### **3. Risks and Benefits**

This is a minimal risk study, and thus we do not anticipate problems beyond our control that involve risks to subjects and others happening.

No clinical assessments will be taken by research staff. Clinical data will be extracted from the EHR system at Piedmont as described above for evaluation and for participant study safety monitoring at 6, 12 and 24-month timepoints and will reflect their processes for routine screenings based on current clinical practice guidelines.

Physical activity: Risks from increased physical activity will be minimized by: 1) recommending physical activity in line with national guidelines; 2) encouraging moderate activity; and 3) directing participants to their physicians when appropriate. If exercise-related symptoms are reported, we will advise participants to get clearance from their PCPs before they can restart physical activity.

Participants will be counseled to change behaviors that will maintain or reduce weight. If individuals follow this advice and decide to change their health behaviors, there should be few risks or side effects. The materials and counseling will provide guidance on preventing and managing the side effects of health behavior change.

Data confidentiality: We will use the standard operating procedures that have been used on our prior trials for survey conduct and data management. All paper files related to the study will be stored in a secure location at Duke University in a locked file cabinet accessible only to key study personnel. The privacy, security, and durability of accumulated personal health information are of paramount importance.

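### On the natural reading of the SAP, the primary percentages, RR and RD come from cutting point EBLUPs at 3% of an undefined baseline, which generally biases them, in a direction that depends on that baseline

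*Combined protocol and SAP*

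**What the plan says.** The protocol (1. Research Design) defines the primary outcome as at most 3% "change in initial body weight over 24 months". The sample-size paragraph refers only to baseline weight. Neither place gives a source or a time window for that weight.

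The SAP first fits a linear mixed model to weight. It then obtains the primary percentages from individual EBLUPs and compares the arms "using both a log-binomial model and linear risk model on the EBLUP output". Two safeguards are described. One is a data requirement: "To ensure good predictions, we only used individual EBLUPs from participants with at least 1 EHR weight documented within a 6-month window" centred on 24 months. The other concerns precision: "The extra variability induced by the EBLUPs being predicted from the model was taken into account using a resampling procedure". The details of the resampling are left to Multimedia Appendices 1 and 2, which were not among the documents supplied.

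The recorded baseline would be a routine clinic weight. Section 2 says "Eligible participants will have had a non-urgent visit to a Piedmont Health clinic within the last 2 weeks", and section 3 says "No clinical assessments will be taken by research staff".

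**The concern.** An EBLUP is shrunk towards the mean, so predicted changes vary less across participants than true changes do. The share of predictions below a cut is then generally not the share of true values below it. If both ends of the change are predicted, shares are too high in an arm whose mean gain is below 3% and too low in an arm above it. If the 24-month prediction is set against the recorded baseline, the visit-level noise in that one weight stays in the change. The spread is then too wide relative to true change, and the error reverses.

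These counts are the primary outcome estimates, and the SAP presents the RD as absolute efficacy. The bias depends on the number of weights per person and not on the number of participants, so a larger sample does not remove it. The 6-, 12- and 18-month comparisons and the widened-window analysis use the same kind of count, so agreement among them would not show that the bias is absent.

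**Working it through.** **Plan figures.** The documents give no figure for this step: no mean change, SD, residual SD, visit rate or expected percentage. The only related figure is 192 per group (section 2, Sample size), inflated to 192 × 1.15 = 220.8, or 221. It is used below only to scale the bias against an SE.

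**Assumed inputs.** Baseline 85 kg (between-person SD 13 kg); SD of 24-month change 4 or 6 kg; residual SD 2 or 3 kg; 1, 2 or 4 weights a year from -18 to 30.5 months, plus one at baseline; everyone has a weight at 21 to 27 months.

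**Formula.** Gain of at most 3% means W24 - 1.03 × W0 ≤ 0. With mean change m, share = Φ((2.55 - m)/S), where 2.55 = 0.03 × 85. For true change with SD 4, S = √(4² + (0.03 × 13)²) = 4.02. For a count of EBLUPs, S² is multiplied by the ratio of the variance of the EBLUP-based contrast to that of the true one. Over the assumed inputs this ratio was 0.60 to 0.94 with a predicted baseline and 1.05 to 1.48 with a recorded one.

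**Worked case** (SD 4, residual SD 3, 1 weight a year; arm means -0.5 intervention, +0.8 usual care):
- True: Φ(3.05/4.02) = 77.6%, Φ(1.75/4.02) = 66.8%.
- Predicted baseline, ratio about 0.60, S = 3.11: about 83.6% and 71.3%. Averaging over simulated visit patterns gives 83.7% and 71.4%.
- Recorded baseline, ratio about 1.33, S = 4.63: 74.5% and 64.7%.

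The same inputs with other arm means (intervention/usual care; RD in points, taken before rounding):

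| Means, kg | True | Predicted baseline | Recorded baseline |
|---|---|---|---|
| -0.5/+0.8 | 77.6/66.8, RD 10.8, RR 1.16 | 83.7/71.4, RD 12.3, RR 1.17 | 74.5/64.7, RD 9.8, RR 1.15 |
| +3.5/+4.8 | 40.7/28.8, RD 11.9, RR 1.41 | 37.9/23.4, RD 14.6, RR 1.62 | 41.9/31.4, RD 10.5, RR 1.34 |
| -5/-3.7 | RD 3.0 | RD 1.5 | RD 3.7 |
| No effect, equal visits | RD 0.0 | RD 0.0 | RD 0.0 |

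**Range over all assumed SDs and visit rates, means -0.5/+0.8 kg.**
- Predicted baseline: shares 0.3 to 6.1 points high, RD +0.2 to +1.6.
- Recorded baseline, against true change: shares 0.3 to 4.2 low, RD -0.2 to -1.4.
- Recorded baseline, against true 24-month weight relative to the recorded baseline: shares 0.1 to 1.8 high, RD +0.1 to +0.6.
- The baseline choice alone moves shares by up to 83.7 - 74.5 = 9.2 points and the RD by up to 12.3 - 9.8 = 2.5. The smallest gaps are about 1.4 and 0.8 points for the shares and 0.5 for the RD.

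**Scale.** With 192 per arm, SE(RD) = √(0.776 × 0.224/192 + 0.668 × 0.332/192) = 4.5 points, so 1.6/4.5 = 0.36. At +3.5/+4.8 kg the SE is √(0.407 × 0.593/192 + 0.288 × 0.712/192) = 4.8 points, the bias is 14.6 - 11.9 = 2.7, and 2.7/4.8 = 0.56. There the baseline choice moves the RD by 14.6 - 10.5 = 4.1.

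**Second model.** A separate simulation (90 kg, one post-enrolment slope, 60,000 per arm, window weight required) agreed. With arm means below 3%, shares were about 1 to 7 points high with a predicted baseline and 1 to 7 low with a recorded one. Averaged conditional probabilities were within about 0.3 points of the truth in every arm.

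**Variances estimated.** In 300 simulated trials of 192 per arm (1 weight a year), the mean true RD was 10.8. The predicted-baseline count gave 12.0 (SD across trials 5.7), the recorded-baseline count 9.8 (5.2), and averaged conditional probabilities with a latent baseline 10.7 (4.3). The Monte Carlo SE of each mean is about 0.3.

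**The case against.** The strongest objection is that the resampling may already solve this. A reader might infer from the SAP that the resampling widens the intervals and leaves the percentages where they were. The stated purpose, extra variability, fits that, and a bootstrap of participants would indeed leave the centre unchanged. But drawing from each participant's predictive distribution and cutting each draw again also fits the wording, and that would move the percentages and remove the bias. Without the appendices the stronger reading is not established. This part of the objection stands.

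Second, the requirement of a weight near 24 months limits shrinkage. It does, but every calculation above imposes it and the bias remains.

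Third, part of the gap between the two baselines is a difference of target. This also stands: against its own target the recorded-baseline count is at most 1.8 points off with means of -0.5/+0.8 kg. The plan does not say which target is meant.

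Fourth, the bias is modest beside the noise. With means of -0.5/+0.8 kg the RR is 1.16, 1.17 or 1.15 in the worked case, and the simulated SD of the RD (5.2 to 5.7 for the counts) exceeds 4.5. If the assumed 5% monthly loss applied to the 192, about 192 × 0.95^24 = 56 per arm would remain and the SE would be about 8.4. That is fair, but the bias is systematic, and it is larger when arm means lie above 3%.

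**Conclusion.** The concern holds on the natural reading of the SAP. The primary percentages, RR and RD rest on dichotomised point predictions with an undefined baseline, and such counts are generally biased. With means of -0.5/+0.8 kg, shares are off by up to about 6 points and the RD by up to about 1.6. Those limits belong to that setting only: at +3.5/+4.8 kg the predicted-baseline RD is about 2.7 too high, and the baseline choice moves it by about 4 points. Every size depends on the assumed SDs, visit rates and means.

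A reader might go further and infer that the plan exaggerates the effect or could create one. The documents do not support that. The RD can be too high or too low, depending on the baseline and on where the arm means lie. With no effect and equal visit density it is unbiased. A spurious RD needs visit density to differ between arms: with no effect and 1 against 2 weights a year, it would be 1.3 points (predicted) or 0.4 (recorded). Nothing suggests such a difference. Of usual care the protocol says "We will not influence usual primary care in any other way", and of weighing "At Piedmont, weight and blood pressure are measured at all visits, including for acute care". The first-stage differences in mean weight change are unaffected.

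**What to change.** 1. State whether the 3% is taken from the recorded or the model-predicted baseline, with source and window, and name the target that follows.
2. Take the point estimates as well as the intervals for the percentages, RR and RD from repeated draws of each participant's joint conditional distribution of baseline and 24-month weight, fitting the risk models on each draw and combining. Averaged conditional probabilities of gain of at most 3% would also serve. Use the latent baseline if true change is the target; draws set against the recorded baseline estimate the other target.
3. Use the same method at 6, 12 and 18 months and in the window sensitivity analysis.
4. Report the number of weights per participant by arm.

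If the appendices already centre the estimates on such draws, only the SAP wording and the baseline definition need correcting. Otherwise the cost is a re-run of the second stage on the existing mixed model, with no new data. The downsides are a little more analysis work, reliance on the model's normality and variance estimates, and possibly less favourable figures.
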